STUDY PROTOCOL PLAN AND STADISTICAL ANALYSIS PLAN (SAP)

UNIVERSITY CEU CARDENAL HERRERA

Principal investigator: [name] [name]

TITLE: Textural Analysis and Effect of ROI Size on Infrared Thermography in Athletes With Patellar Tendinopathy. A Cross-sectional Study

Research and Ethics Committee of University Católica San Antonio, Number: CE111803

NCT ID:

DATE: 07-23-2025

STUDY PROTOCOL PLAN

Objectives:

The objectives of our study have been the following:

The objectives of this study were: (1) to evaluate differences in thermal and GLCM-based textural features between athletes with PT and healthy controls; (2) to compare the diagnostic performance of IT and GLCM features applied to thermographic images; and (3) to identify the most appropriate ROI size for optimal characterization of PT using both thermal and textural analysis.

Volunteers who want to participate in the study will read the general information of the study and sign the informed consent to participate in the study.

Once the informed consent has been read and delivered, the evaluator will check that they meet the inclusion criteria.

Participants will be divided into two groups: (1) athletes with unilateral PT, diagnosed using a combination of clinical criteria, specific functional tests, and ultrasound evaluation. Additional inclusion criteria for this group included a symptom duration of more than 3 months, a VISA-P score of less than 80, and a differential diagnosis to rule out other possible causes of anterior knee pain; (2) healthy volunteer athletes, recruited under the inclusion criteria of no previous history of PT and a VISA-P score of 100.

Participants with any other lower limb pathology, nerve or vascular disorder, or skin lesion in the knee area that could alter the thermal information of the patellar tendon region will be excluded from both groups.

All participants were instructed not to engage in physical exercise; not to drink alcohol, coffee or energy drinks 12 hours before the measurements; not to smoke in the previous 6 hours; not to apply creams or lotions to their legs to avoid altering skin emissivity; to report any medication or treatments they were taking; and to try to avoid altering their rest and meal habits. These requirements minimise the influence of individual extrinsic factors on the IT results.

Recorded variables

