Demographic and clinical characteristics (gender, age, BMI, and duration of evolution) will be recorded. The severity of patellar tendinopathy will be measured using the widely accepted and valid Victorian Institute of Sport Assessment-Patella (VISA-P) questionnaire. All thermal image recordings were performed by the same researcher.

Determination of sample size

The sample size will be calculated using G*Power v.3.1.9.7 software (Heinrich-Heine University) for a logistic regression design to evaluate the diagnostic accuracy of IT in distinguishing between patients with PT and healthy controls, taking into account the possible inclusion of covariates. The parameters are set as follows: odds ratio = 5, alpha error probability $\alpha = 0.05$, power $1-\beta = 0.80$, R^2 for other covariates = 0.1, binomial distribution with a proportion $\pi = 0.5$.

Image acquisition protocol

TI images will be recorded with an OPTRIS PI 450 IRT camera coupled to Optris PI Connect software (Germany). The IRT camera has a noise equivalent temperature difference <40 mK with a field of view of $38^\circ \times 29^\circ$, a wide temperature range of -20 °C to $+100$ °C, a spectral range of $7.5-13$ μ m, a focal plane array sensor size of 382×288 pixels, an emissivity set to 0.98, and a measurement uncertainty of $\pm 2\%$ of the global temperature reading. The capture frame size was 55.4×40.63 cm (1.5 mm/px).

The participant will acclimatise in an isolated room (3.86×3.47 m²), without temperature sources, at an average temperature of (23.7 ± 0.9 °C) and relative humidity of ($49 \pm 5\%$) for 15 minutes without clothing on the lower extremities. The participant will sit on a hydraulic stretcher with their feet on a step to isolate contact with the floor, and the camera will be positioned perpendicular to the subjects for a more accurate reading. Two rectangular ROIs will be selected on each knee using a previously described method by superimposing ROIs on thermal images using markers on the skin. a) an ROI of the patellar tendon (tendon ROI); b) an ROI of the anterior part of the knee (knee ROI) using the anatomical references of the upper pole of the patella, anterior tibial tuberosity, and lateral contour of the knee.

Statistical Analysis Plan (SAP)

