The data will be analysed using IBM SPSS Statistics for Windows v.25.0 (IBM Company, 2017). The normality and homoscedasticity of the variables will be checked. The data will be summarised using absolute and relative frequencies for categorical variables, and means \pm standard deviations (SD) and 95% confidence intervals for continuous variables.

Independent sample t-tests will be used to compare continuous variables, and a chi-square test will be used to compare categorical variables at baseline between PT patients and controls.

One-way analysis of covariance will be used to analyse the thermal difference and textural characteristics between PT patients and healthy controls, controlling for the effects of clinical and demographic covariates. Cohen's d statistic will be calculated to assess the effect size (d > 0.1 small, around 0.3 medium, and >0.5 large).

To calculate the diagnostic accuracy of the thermal difference and textural characteristics based on first- and second-order statistical analysis, simple logistic regression will be performed for age, sex, and BMI by group, including them in subsequent models if $p < 0.20$. Sensitivity (Se), specificity (Sp) and Youden's index (expressed as $Se + Sp - 1$) will be investigated, as well as the positive and negative likelihood ratios (LRp and LRn) of thermal difference, textural characteristics and their combinations. The thermal difference and textural characteristics will be introduced one by one and in all possible combinations (255 models) in the logistic regression analyses, including a maximum combination model containing all characteristics.

Receiver operating characteristic (ROC) curves will be used and the Hosmer-Lemeshow goodness-of-fit test will be performed by comparing the observed and expected frequencies of the outcome variable ($p > 0.05$ indicates a good fit). The Brier score will be calculated to evaluate the accuracy of the probabilistic predictions, where lower scores indicate better model performance. An area under the curve (AUC) value close to 90% and sensitivity and specificity values above 80% are considered acceptable.

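### The accuracy benchmark is tied to no model, ROI, selection rule or validation, so one of 255 or more fitted models can clear it by chance or overfitting

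*Combined protocol and SAP*

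**What the plan says.** The diagnostic-accuracy paragraph of the Statistical Analysis Plan (SAP) sets out the search: "The thermal difference and textural characteristics will be introduced one by one and in all possible combinations (255 models) in the logistic regression analyses". The model with every characteristic is listed as a member of that set and is given no special standing. Each model is described by sensitivity, specificity, Youden's index, likelihood ratios, ROC curve, Hosmer-Lemeshow test and Brier score. Age, sex and BMI enter later models if they reach p < 0.20.

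The last sentence of the SAP gives the benchmark: "An area under the curve (AUC) value close to 90% and sensitivity and specificity values above 80% are considered acceptable". It refers to point values, with no confidence bound, and the AUC limit is not an exact number.

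Under Image acquisition protocol, "Two rectangular ROIs will be selected on each knee" (tendon and knee). The third objective is "3) to identify the most appropriate ROI size for optimal characterization of PT using both thermal and textural analysis", so the ROI is itself an outcome of the analysis.

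The plan does not name a primary model or ROI, a rule for choosing among models, a multiplicity adjustment, an exploratory label, or any bootstrap, cross-validation or hold-out sample. It lists the inputs to the sample size calculation but not the resulting N.

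**The concern.** A benchmark protects against over-claiming only if it is clear beforehand which result is held against it. Here any of the fitted models may be, and each is judged on the data that produced its coefficients and possibly its cut-off. Two mechanisms push the best figures upwards. One is overfitting within a model of up to eight markers (plus covariates) in a small sample. The other is selection of the most favourable result across many models and possibly two ROIs. The second survives cross-validation of each model separately, because the maximum of many honest estimates is still biased upwards.

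At stake is whether the reported AUC, sensitivity and specificity would hold in new athletes, and whether the preferred ROI reflects a real advantage.

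**Working it through.** **1. The plan's own figure.** All non-empty subsets of k features number 2^k − 1. With k = 8, 2^8 − 1 = 255, which reproduces the SAP. Refitting in each of two ROIs gives 2 × 255 = 510. The SAP does not say that 255 is per ROI, so both counts are carried below.

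**2. Sample size implied by the stated inputs.** Determination of sample size gives odds ratio 5, α = 0.05, power 0.80, R² = 0.1 and a binomial predictor with proportion 0.5. It does not give sidedness or the baseline probability p1. With p2 = 5·p1/(1 − p1 + 5·p1), the Wald form is

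N = (z_α + z_β)² · [1/(0.5·p1(1−p1)) + 1/(0.5·p2(1−p2))] / (ln 5)² / (1 − 0.1).

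- Two-sided, p1 = 0.5, p2 = 0.833: 7.849 × (8 + 14.4) / 2.590 / 0.9 = 75.4, so 76.
- Two-sided, p1 = 0.1, p2 = 0.357: 7.849 × (22.22 + 8.71) / 2.590 / 0.9 ≈ 104.1, so 105.

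The Hsieh form, one-sided, with cases half of the total (p1 = 0.309, p2 = 0.691), gives the smallest value: (1.645·√(0.25/0.5) + 0.8416·√(2 × 0.2135))² / (0.382² × 0.5) / 0.9 ≈ 44.7, so 45. The two-sided version gives 58. The bracket is therefore about 45 to 105, and 46, 58 and 76 were simulated.

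**3. What truly missing the benchmark means.** For two normal score distributions of equal spread, d = √2·Φ⁻¹(AUC) and Se = Sp = Φ(d/2) at the Youden point.

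| True AUC | d | Se = Sp |
|---|---|---|
| 0.75 | 0.954 | 68% |
| 0.80 | 1.190 | 72% |
| 0.85 | 1.466 | 77% |
| 0.90 | 1.812 | 82% |

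A full marker set with true AUC 0.85 or less falls short of 80% sensitivity and specificity. In this setting no subset can truly do better than the full set, so every pass is a false one.

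**4. Chance of a pass on apparent accuracy.** Assumptions: equal groups; eight normal markers per ROI with correlation 0.5 and mixed signal strengths; the same marker correlated 0.7 between ROIs; linear discriminant in place of logistic regression; Youden cut-off; pass if AUC ≥ 0.90 with Se and Sp > 80%. There were 1,500 runs per row, with Monte Carlo error of at most about ±2.5 percentage points. The last column uses 10-fold cross-validation.

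| N | True AUC | Any of 255 | Any of 510 | Named eight-marker model, in-sample | Same model, cross-validated |
|---|---|---|---|---|---|
| 46 | 0.75 | 11.1% | 18.8% | 6.9% | 0.2% |
| 46 | 0.80 | 25.5% | 38.7% | 16.3% | 0.7% |
| 46 | 0.85 | 53.9% | 70.8% | 36.1% | 2.9% |
| 58 | 0.75 | 6.1% | 10.4% | 3.5% | 0.0% |
| 58 | 0.80 | 17.4% | 27.9% | 11.0% | 0.6% |
| 58 | 0.85 | 44.1% | 59.3% | 28.9% | 3.1% |
| 76 | 0.75 | 1.3% | 2.5% | 0.9% | 0.0% |
| 76 | 0.80 | 8.5% | 13.3% | 5.1% | 0.1% |
| 76 | 0.85 | 31.7% | 44.2% | 21.7% | 2.9% |

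Reading the AUC limit as 0.88 raises any-of-510 to 26–53% at true AUC 0.80 and 63–82% at 0.85. At N = 120 (300 runs, cut-off 0.90) the rates are 0%, 4% and 26% for true AUC 0.75, 0.80 and 0.85. Fitting actual logistic models at N = 58, true AUC 0.80 (250 runs) gave 24% for any of 510, against 28% above.

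**5. Selection alone.** With every model scored by leave-one-out, N = 60, true AUC 0.85, cut-off 0.88 and equally informative markers, any of 510 passed in about 28–37% over repeated runs and marker correlations of 0.3 to 0.7; one 200-run check gave 38.5%. Any of 255 passed in 15–22%, and one named all-marker model in about 1–4%. With unequal marker strengths, any-of-510 was 16% against 2%. With true AUC 0.80 it fell to about 3–10%.

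**The case against.** The closing sentence can be read as an interpretive label, like the effect-size bands for Cohen's d and the Hosmer-Lemeshow p-value guide in the same section. The objectives ask for group differences, a comparison of diagnostic performance and the best ROI. None asks whether the method is acceptable, and no go/no-go rule is written. That is fair, and it means there is no formal error rate that the plan promises to control. It does not remove the problem: the label will be attached to some model, and nothing limits which one.

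A reader might infer that 510 models face the benchmark. That is the natural reading, since objective 3 needs both ROIs analysed, but the SAP states only 255 and does not list the features. Eight features in total, such as four from each ROI, would fit equally well. The concern stands with 255.

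A reader might also infer that a falsely favourable result is likely whatever the truth. The documents do not support that: they give neither N nor the true accuracy, and the rate is low when the markers fall well short and N is towards the upper end of the range. Nor does the SAP describe leave-one-out, so the figures in step 5 of the working isolate the selection effect and do not describe the plan as written.

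Finally, part of the inflation is overfitting and not multiplicity. This is correct, and it shapes the fix: naming a model while keeping its in-sample accuracy still gives 22–36% at true AUC 0.85.

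**Conclusion.** The concern holds in conditional form. As written, the plan yields upwardly biased accuracy and leaves open which result earns the favourable label. For a near miss (true AUC 0.80 to 0.85) with N of 46 to 76 and an AUC cut-off of 0.90, at least one model clears the benchmark in-sample in roughly 9–54% of studies if there are 255 models, and 13–71% if there are 510. One pre-named eight-marker model judged on cross-validated accuracy would do so in about 0.1–3.1%.

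These sizes rest on an assumed N, normal markers, the assumed correlations and signal pattern, and a numerical reading of the AUC limit. Other patterns at N = 60 and true AUC 0.80 gave 19–26% for any of 510. The covariates admitted at p < 0.20 were not simulated and would add parameters. The missing decision rule and validation do not depend on any of these assumptions.

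**What to change.** Write the AUC benchmark as a number in the SAP and apply it, with the sensitivity and specificity limits, only to optimism-corrected accuracy. Then choose one of two routes:

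- **(a)** Name one model in one ROI before analysis and judge it on cross-validated or bootstrap-corrected AUC, sensitivity and specificity.
- **(b)** If the best model found is to be judged, apply the benchmark to the whole selection procedure. The choice of features, ROI, cut-off and p < 0.20 covariates must then be repeated inside each resample.

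Under either route, report all other models and the other ROI as exploratory, without a verdict against the benchmark. State also whether 255 is the count per ROI or in total.

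This needs a few sentences in the SAP and no new data or participants. The costs are extra analysis work, lower reported accuracy and a lower chance that a truly adequate marker set passes. If the named model is the eight-marker one, that last cost is large: with true AUC 0.92 (Se = Sp about 84%) and N = 60, its cross-validated accuracy passed in only about 24% of runs. A smaller named model, or route (b), may therefore be preferred.
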